## 1.2 Purpose

The main purpose of the study is to support dose selection for future Phase 3 clinical trials by evaluating the efficacy and safety of four MIJ821 doses (0.0048, 0.016, 0.048 and 0.16 mg/kg) administered every other week by intravenous infusion on top of pharmacological antidepressant treatment, compared with placebo plus pharmacological antidepressant treatment, for the rapid reduction of the symptoms of MDD in participants who have suicidal ideation with intent. In addition, the study will explore the effect of single dose administration of MIJ821 0.16 and 0.048 mg/kg to treat MDD in participants who have suicidal ideation with intent.

The study will also have a 12-month Extension Period to explore durability of the effect of the study treatment and the effect of MIJ821 on relapses rate, as well as safety of repeated MIJ821 administration.

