## 3 Study design

This is a Phase 2b double-blind, placebo-controlled, randomized, parallel-group dose-ranging trial to investigate the efficacy and safety of four doses of intravenous MIJ821 administered as a 40-min infusion in addition to comprehensive standard of care (SoC) for the rapid reduction of the symptoms of MDD in participants who have suicidal ideation with intent. Comprehensive SoC includes initial hospitalization and pharmacological antidepressant therapy (antidepressant monotherapy or an antidepressant plus augmentation). In addition, the study will also explore the effect for single dose administration of 0.16 mg/kg and 0.048 mg/kg given once to treat MDD in participants who have suicidal ideation with intent.

Participants meeting the eligibility criteria will be randomized in a 2:1:2:2:2:2 ratio to treatment with:

[figure not shown]
- placebo every other week
- MIJ821 0.0048 mg/kg every other week
- MIJ821 0.016 mg/kg every other week

- MIJ821 0.048 mg/kg every other week
- MIJ821 0.16 mg/kg every other week
- MIJ821 0.048 mg/kg single infusion with two subsequent placebo dosages given every other week
- MIJ821 0.16 mg/kg single infusion with two subsequent placebo dosages given every other week

On the top of ongoing pharmacological antidepressant SoC treatment. In all treatment arms, investigational treatment will be administered by intravenous infusion every other week, three infusions in total during the placebo-controlled double-blind Core, 6-week period of the study.

The study consists of three periods: a Screening Period (up to 48 hrs), a double-blind Core Period (6 weeks) and Extension Period (up to 52 weeks).

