### **8.5.3 Pharmacokinetics**

Pharmacokinetic (PK) samples will be collected at the time points defined in the Assessment Schedule ([Table 8-1](#)). All times defined for PK sample collection refer to the start of infusion defined as time 0 h. Instructions are outlined in the central laboratory manual regarding sample collection, numbering, processing and shipment. Refer to [Section 8.5.4.1](#) for information regarding the potential use of residual samples.

It has to be emphasized, that all PK samples **must be collected from the contralateral arm of the infusion site.**

In order to better define the PK profile, the timing of the PK sample collection may be altered based on emergent data. The number of samples/blood draws and total blood volume collected will not exceed those stated in the protocol.

PK samples should be collected in all patients to avoid unblinding. Only samples from patients treated with MIJ821 will be analyzed.

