### **Pharmacokinetic parameters**

[figure not shown]
If data permit, the following pharmacokinetic parameters of MIJ821 will be determined after the first infusion using the actual recorded sampling times and non-compartmental method(s) with Phoenix WinNonlin (Version 8 or higher):

Following first infusion, AUClast, Cmax, Tmax, and if feasible T1/2 will be determined from the plasma concentration-time data. If PK data allow, secondary PK parameters will be estimated like AUC0-24h (or other AUC values across a defined period), AUCinf, CL, Vz (but not limited). Following all other infusions, Cmax and Tmax will be determined.

The linear trapezoidal rule will be used for AUC calculation. Regression analysis of the terminal plasma elimination phase for the determination of T1/2 will include at least 3 data points after Cmax. If the adjusted R^2 value of the regression analysis of the terminal phase will be less than 0.75, no values will be reported for the secondary PK parameters like T1/2, AUCinf, Vz and CL, or other parameter dependent on estimation of the terminal phase.

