#### **12.5.3 Pharmacokinetics**

MIJ821 plasma concentrations will be expressed in mass per volume. The plasma concentrations will be listed by treatment, subject number, and visit/sampling time point. Descriptive summary statistics will be provided by treatment and visit/sampling time point, including the frequency (n, %) of concentrations below the LLOQ and reported as zero.

Summary statistics of plasma concentrations will include mean (arithmetic and geometric), SD, CV (arithmetic and geometric), median, minimum and maximum. Concentrations below LLOQ will be treated as zero in summary statistics and for PK parameter calculations. A geometric mean will not be reported if the dataset includes zero values.

Pharmacokinetic parameters will be calculated as described in [Section 8.5.3](#) and will be listed by treatment and subject number. Descriptive summary statistics of pharmacokinetic parameters will include mean (arithmetic and geometric), SD, and CV (arithmetic and

geometric), median, minimum and maximum. An exception to this is Tmax where median, minimum and maximum will be presented.

The dose proportionality of MIJ821 for PK parameters such as Cmax and AUClast (or other AUCs) will be explored for PK parameters collected after the 1st infusion. The selection, which of the AUC values will be used, depends on the determinability of plasma concentration above LLOQ and the estimation of comparable AUC values across the cohorts.

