**Table 12-2 Non-compartmental pharmacokinetic parameters**

AUClast	The AUC from time zero to the last measurable concentration sampling time (tlast) (mass x time x volume-1)
AUCinf	The AUC from time zero to infinity (mass x time x volume-1)
AUC0-24h	Area under the curve from time zero to 24 h after start of infusion (mass x time x volume-1)
Cmax	The maximum (peak) observed plasma, blood, serum, or other body fluid drug concentration after single dose administration (mass x volume-1)
Tmax	The time to reach maximum (peak) plasma, blood, serum, or other body fluid drug concentration after single dose administration (time)
Lambda_z	Smallest (slowest) disposition (hybrid) rate constant (time-1) may also be used for terminal elimination rate constant (time-1)
T1/2	The elimination half-life associated with the terminal slope ( $\lambda_z$ ) of a semi logarithmic concentration-time curve (time). Use qualifier for other half-lives
CL	The total body clearance of drug from the plasma (volume x time-1)
Vz	The apparent volume of distribution during terminal phase (volume)

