1.2 Study objectives and endpoints

Table 1-1 Objectives and Related Endpoints

Objective(s)	Endpoint(s)
Primary objective(s)	Endpoint(s) for primary objective(s)

• Core: To investigate dose response relationship for 4 doses of MIJ821 vs. placebo	
• Change from baseline in MADRS total score at 24 hours after the start of the first infusion
Secondary objective(s)	Endpoint(s) for secondary objective(s)

• Core: To assess safety and tolerability of MIJ821	
• Number and severity of treatment-emergent adverse events (TEAEs), including AEs of special interest in Core Period

• Core and Extension: To assess the effect of MIJ821 on sustained response and remission	
• Proportion of participants meeting response criteria ($\geq 50\%$ reduction from baseline in MADRS total score) over time in Core Period.• Proportion of participants meeting criteria for sustained response ($\geq 50\%$ reduction from baseline in MADRS total score sustained for a period of at least four weeks) in Core Period• Proportion of participants meeting remission criteria (MADRS total score of ≤ 12) over time in Core Period• Proportion of participants meeting criteria for sustained remission (MADRS total score of ≤ 12 sustained for a period of at least four weeks) in Core Period• Proportion of participants meeting criteria for relapse over all randomized population over fixed period in Extension Period• Proportion of relapsing participants meeting response criteria or remission criteria after the first infusion of MIJ821 retreatment in Extension Period

• Core and Extension: To assess MIJ821 pharmacokinetics in plasma	
• PK parameters of MIJ821 in plasma after 1st infusion described by AUClast, Cmax, Tmax (parameters not limited) and after each infusion described by Cmax and Tmax

Objective(s)	Endpoint(s)

Objective(s)	Endpoint(s)

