2.7 PK analyses

Variables

The following PK parameters will be determined using the actual recorded sampling times and non-compartmental method(s) with Phoenix WinNonlin (Version 8.0 or higher):

- Following first infusion in Core Period:
 - AUClast, Cmax, and Tmax will be determined from the plasma concentration-time data.
 - If data allow, secondary PK parameters will be estimated like T1/2, AUC0-t (t represent the end of the observation period of interest), AUCinf, CL, Vz (list of parameters are not limited).
- Following all other infusions in Core Period and all infusions in Relapse Retreatment Period:
 - PK samples will be collected at pre-dose (if scheduled), 40 min (end of infusion), and 4 h after end of infusion. The PK sample at the end of infusion (40 min) represents the Cmax and Tmax values. No other PK parameters will be estimated.

Descriptive analyses

All MIJ821 plasma concentrations and PK parameters including their descriptive statistics will be presented with three significant figures for Core Period and Relapse Retreatment Period. The exception will be %CV (Coefficient of Variation) values, which will be reported to one decimal place and N values, which will be reported as whole integers.

For the summary statistics of plasma concentration, the following time windows are defined: predose:

Table 2-11 Time window for plasma concentration

Nominal time after start of infusion	Elapsed time after start of infusion
0	All times before start of infusion
20 min	20 min +/- 2 min
40 min	40 min +/- 2 min
4 hours	4 hours +/- 30 min
24 hours	24 hours +/- 1 hour

Concentrations collected outside of the time windows will be not used for summary statistics of plasma concentrations. The time windows will be used for all infusions. For the PK parameter estimation, all concentrations with a recorded elapsed time will be used.

Summary statistics of plasma concentrations and PK parameters will be provided on separate tables and will include: mean (arithmetic and geometric), SD, CV (arithmetic and geometric), median, minimum and maximum, N value, by dose(/regimen) and study period. Concentrations below LLOQ (Lower Limit of Quantification) will be treated as zero in summary statistics and for PK parameter calculations. A geometric mean will not be reported if the dataset includes zero values. An exception to this is Tmax where median, minimum and maximum will be presented.

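### The plain linear trapezoidal rule overstates AUClast whenever the 24 h sample is measurable, because no PK sample lies between 4 h and 24 h; linear-up/log-down would remove most of the bias

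*Protocol*

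**What the plan says.** Protocol 8.5.3, under PK parameters, fixes the integration rule for every AUC: "The linear trapezoidal rule will be used for AUC calculation". SAP 2.7 names no rule, and SAP section 4 declares no change from the protocol's analyses, so the linear rule carries over.

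The SAP lists the affected endpoint among its secondary endpoints: "PK parameters of MIJ821 in plasma after 1st infusion described by AUClast, Cmax, Tmax (parameters not limited". Protocol Table 12-2 defines AUClast as "The AUC from time zero to the last measurable concentration sampling time (tlast".

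SAP Table 2-11 lists pre-dose, 20 min, 40 min and 4 h, and then "24 hours +/- 1 hour". The PK row of Protocol Table 8-1 could not be read in the copy used, but the column headings of that table also show no time between 4 h and 24 h. Protocol 8.5.3 adds that "the timing of the PK sample collection may be altered based on emergent data", without allowing more samples.

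For values below the LLOQ (0.1 ng/mL), Protocol 12.5.3 says: "Concentrations below LLOQ will be treated as zero in summary statistics and for PK parameter calculations". The same section plans to explore dose proportionality after the first infusion using Cmax and AUClast or another AUC. It leaves the choice of AUC to what can be determined above the LLOQ and compared across dose groups.

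**The concern.** After the infusion ends, plasma concentration falls along a convex curve. A straight line between two points on such a curve lies above it, so the linear rule can only overstate the area, and a 20 h interval gives it room to do so. The direction of the error is therefore known wherever the 24 h sample is measurable. Only its size is open.

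Two things are at stake. The first is the level of a named secondary endpoint. The second is comparison between patients. The error is larger for short half-lives than for long ones, so patients who clear the drug slowly look less different from the rest than they are. Protocol 6.2.1 makes this relevant: it predicts 64% of elimination through CYP2D6, permits CYP2D6 inhibitors, reports that about 70% of patients in the proof-of-concept study took at least one, and cites simulated increases of up to 2-fold in AUC against up to 1.3-fold in Cmax with fluoxetine or paroxetine. AUC rising more than Cmax points to slower elimination.

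**Working it through.** The plan states no AUC, half-life or clearance, so there is no figure of its own to reproduce. The calculation below gives a range.

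**Inputs from the documents.** Infusion length: "four doses of intravenous MIJ821 administered as a 40-min infusion", so T = 2/3 h. Sampling times from SAP Table 2-11: 0, 1/3, 2/3, 4 and 24 h. LLOQ: 0.1 ng/mL (Protocol 8.5.3). Dose range: "four MIJ821 doses (0.0048, 0.016, 0.048 and 0.16 mg/kg" mg/kg), which spans 0.16/0.0048 = 33.3-fold.

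**Assumptions.** One compartment, half-life 2 to 24 h, k = ln 2 / half-life. With Cmax scaled to 1, C(t) = (1 − e^(−kt)) / (1 − e^(−kT)) during the infusion and e^(−k(t−T)) afterwards.

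**Step 1: the 4–24 h piece.** For an exponential decline, linear/true = ((r + 1)/2) × ln r / (r − 1), where r = C4/C24 = e^(20k). At a half-life of 4 h, r = 2^5 = 32, and 16.5 × 3.466 / 31 = 1.84.

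**Step 2: the whole profile at a half-life of 4 h.** The concentrations are 0, 0.5144, 1, 0.5612 and 0.0175. The linear areas are 0.0857 + 0.2524 + 2.6021 + 5.7877 = 8.728. The true area is 2.872 (0–4 h) + 3.138 (4–24 h) = 6.009. The ratio is 8.728/6.009 = 1.45. If the 24 h sample is below the LLOQ, AUClast ends at 4 h and the ratio is 2.940/2.872 = 1.02.

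**Step 3: the range.**

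| Half-life | C24/Cmax | 4–24 h piece, linear/true | 24 h measurable: linear AUC to 24 h | 24 h below LLOQ: linear AUC to 4 h |
|---|---|---|---|---|
| 2 h | 0.0003 | 3.47 | +76% | +9% |
| 4 h | 0.0175 | 1.84 | +45% | +2% |
| 6 h | 0.0675 | 1.41 | +26% | +1% |
| 8 h | 0.1324 | 1.24 | +17% | +1% |
| 12 h | 0.2598 | 1.11 | +8% | under 1% |
| 24 h | 0.5097 | 1.03 | +2% | under 1% |

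Linear-up/log-down on the same samples is within 0.1% of the true AUC to 24 h in every row.

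**Step 4: between-patient ratios.** Halve clearance at the same dose and volume. From 4 h to 8 h half-life, the true AUC0-24h ratio is 1.77. The linear rule gives 1.77 × 1.166/1.452 = 1.42, and log-down gives 1.77. From 6 h to 12 h, the figures are 1.59 (true), 1.37 (linear) and 1.59 (log-down).

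**Step 5: dose proportionality.** This regresses log AUC on log dose for truly proportional kinetics (slope 1), assuming a top-dose Cmax of 20, 50 or 100 ng/mL.

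- 24 h measurable at all four doses: the bias is one common factor and the slope is 1.00 under either rule.
- Low doses below the LLOQ at 24 h: the AUClast slope is 1.28–1.37 with the linear rule and 1.19–1.30 with log-down. The linear rule adds about 0.04–0.12; the rest comes from AUClast ending at different times.
- AUC0-4h: the slope is 1.00 throughout.

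**Step 6: a second model.** This adds an assumed 0.5 h distribution half-life, with terminal half-lives of 4–24 h. AUC to 24 h is 6–62% high with the linear rule and 3–14% high with log-down. Part of this arises between 40 min and 4 h, where the linear piece is 18–61% high. The small errors in the last column of the table therefore hold for one compartment only.

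**The case against.** **The size is not shown.** No half-life or total plasma concentration is given, and at 12–24 h the error is only 8% to 2%. This stands: a material error is possible, not demonstrated.

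**The largest figure rarely applies to AUClast.** A reader might take +76% at a half-life of 2 h as the possible error in the endpoint. In that row Cmax/C24 is 3,251, so the 24 h sample exceeds 0.1 ng/mL only if Cmax is at least 325 ng/mL. For the lowest dose that means 325 × 33.3, or about 10,800 ng/mL, at the top dose. Otherwise AUClast stops at 4 h and the error is +9%. The objection stands, and the 76% figure should not be used.

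**Dose proportionality.** A reader might infer that the linear rule invalidates this check. The documents do not support that. A common bias factor cancels. Where the slope is distorted, truncation at the LLOQ is the main cause, and log-down does not cure it. Protocol 12.5.3 already lets the analyst use a comparable AUC, and the check is only exploratory. What remains is that the interval is not named and the choice is made after the data are seen.

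**Zero at 24 h.** Entering a zero for a value below the LLOQ might also look harmful. It is not a reason for change: the AUC0-24h slope with zeros is 1.00–1.03.

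**Method preference.** The linear rule is pre-specified and reproducible, and log-down looks near-perfect in the one-compartment model because that model is mono-exponential after the infusion. This is fair, but log-down is also closer to the truth in the two-compartment check.

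**Conclusion.** The point holds, with minor weight. If the 24 h sample is measurable, the linear rule overstates AUClast after the first infusion by about 45% at a half-life of 4 h, falling to 2% at 24 h, and it understates exposure differences between slow and fast clearers. If the 24 h sample is below the LLOQ, the one-compartment bias is about 2% or less for half-lives of 4 h or more, and about 9% at 2 h. These sizes rest on an assumed one-compartment model, the nominal times in SAP Table 2-11 and a range of assumed half-lives. The direction rests only on a convex decline.

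Dose proportionality is affected only if half-life or the last measurable time differs by dose. PK is one input to dose selection at the interim analysis, but a factor common to all doses leaves dose comparisons unchanged. The primary endpoint and the sample size are not affected.

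**What to change.** Replace the linear rule in Protocol 8.5.3 with linear-up/log-down, and state the same rule in SAP 2.7, which at present names none. This is one setting in WinNonlin and one sentence in each document, with no new samples or data.

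As a secondary step, name in advance the common-interval AUC for dose proportionality, for example AUC0-4h, to be used when the 24 h sample is below the LLOQ at any dose. This turns the discretion in Protocol 12.5.3 into a rule.

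There are two costs. AUCs become less directly comparable with any from earlier studies that used the linear rule; reporting both once would bridge that. Log-down also remains inexact if there is a fast distribution phase (3–14% high in the two-compartment check).

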## **9 Study discontinuation and completion**

### **9.1 Discontinuation and completion**

#### **9.1.1 Study treatment discontinuation and study discontinuation**

Discontinuation of study treatment for a participant occurs when study treatment is stopped earlier than the protocol-planned duration. Discontinuation of study treatment can be initiated by either the participant or the investigator.

Discontinuation of study treatment may or may not include study drug infusion interruption, i.e. shortening of the infusion to less than 40 minutes. If the duration of an infusion is shortened, the next planned infusion should be planned to be administered for the full 40 minutes. If there is a concern that the participant cannot tolerate the full duration of the infusion the investigator should consider permanent discontinuation of study treatment.

The investigator must discontinue study treatment for a given participant if, he/she believes that continuation would negatively impact the participant's well-being.

Study treatment must be discontinued under the following circumstances:

- Participant/guardian decision
- Pregnancy
- Use of prohibited treatment as per recommendations in the prohibited treatment [Section 6.2.2](#)
- Any situation in which study participation might result in a safety risk to the participant
- Following emergency unblinding
- Severe hypersensitivity reaction such as anaphylaxis
- Adverse events (including AESI, see [Section 10.2.5](#)), abnormal laboratory values or abnormal test result that indicate a safety risk to the participant
- Lack of study treatment effect based on Investigator's judgement
- Patients meeting the discontinuation criteria for liver laboratory triggers or renal alert criteria as defined in [Table 16-4](#) and [Table 16-5](#)

- Study treatment should also be discontinued for any one of the following treatment-emergent events:
  - Absolute QTcF > 500 msec, confirmed by repeat ECG measurements
  - Resting heart rate < 30 or > 120 bpm
  - QRS > 120 msec and increase > 25% from Baseline (Day 1)
  - Sustained ventricular tachycardia lasting 30 sec or more, ventricular fibrillation, or any hemodynamically compromising cardiac arrhythmia
  - New complete heart block (Grade III AV block) or Second degree AV block Mobitz type II
  - Post-dose systolic blood pressure of  $\geq 200$  mmHg and/or the DBP is  $\geq 120$  mmHg confirmed by triplicate reading (at least one value should confirm the blood pressure increase above the defined thresholds).

If discontinuation of study treatment occurs, the investigator should make a reasonable effort to understand and record the primary reason for the participant's premature discontinuation of study treatment.

Participants who discontinue study treatment or who decide they do not wish to participate in the study further should NOT be considered withdrawn from the study UNLESS they withdraw their consent (see [Section 9.1.2](#)). Where possible, they should return for the assessments indicated in the Assessment Schedule. If they fail to return for these assessments for unknown reasons, every effort (e.g. telephone, e-mail, letter) should be made to contact the participant/pre-designated contact as specified in the lost to follow-up section.

If the participant cannot or is unwilling to attend any visit(s), the site staff should maintain regular telephone contact with the participant, or with a person pre-designated by the participant. This telephone contact should preferably be done according to the study visit schedule.

Following study treatment discontinuation (no further infusions planned), participants should be followed for two months beyond the 6 week Core Period (Follow-up Period).

Participants who discontinue study treatment during the Core Period should return at every scheduled visit until the End of the 6 week Core Period. The list of assessments should be kept as planned with the following exceptions: ECG and vital signs to be measured (triplicates required), no PK sampling collection, and all assessments that are repeated several times in one day should be done only once [REDACTED]

[REDACTED] Participants will then enter the two months Follow-up Period.

Participants who discontinue study retreatment during the Extension Period should return for the End of Relapse visit and subsequently enter the two month Follow-up Period.

If an onsite visit is not possible, then telephone visits should be conducted and collected at minimum the following:

- New / concomitant treatments
- Adverse Events / Serious Adverse Events

The investigator must also contact the IRT to register the participant's discontinuation from study treatment.

If discontinuation occurs because the treatment code has been broken, please refer to Emergency breaking of the treatment code [Section 6.6.3](#).

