2.1.3 Analysis sets

The Randomized Set (RAS) consists of all randomized participants. The descriptions of population will be based on RAS.

The Full Analysis Set (FAS) comprises all randomized participants who received at least one dose of randomized study treatment. Participants will be analyzed according to the treatment they have been assigned to during the randomization procedure. The primary efficacy analysis for data in Core Period will utilize this analysis set.

The Safety Set (SAF) includes all participants who received at least one dose of study treatment. Participants will be analyzed according to the treatment received. In case participants take the wrong treatment (different with the assigned treatment), the first treatment received will be used in analysis. Safety analysis for data in Core Period will be based on SAF.

The Extension Set (ENS) is defined to include all subjects who joined Extension Period. Data collected during follow-up period will be analyzed based on ENS, and grouped by the assigned treatment in Core Period. In case participants take the wrong treatment during Core, the first actual treatment taken will be used for the analysis of safety data only. The analysis of data collected during extension period (before and after re-treatment period) will be based on ENS.

The Retreatment Set (RTS) is defined as a subset of SAF including participants who received at least one dose for the retreatment of relapse. Participants will be analyzed according to the treatment received for the first injection during the Retreatment Period. The efficacy and safety endpoints pertinent to Retreatment Period (see [Table 2-1](#)) will be analyzed based on RTS.

PK Analysis Set (PKS) includes all participants who provided at least one evaluable PK concentration. Determined PK concentrations may be excluded from the PKS (per the scientific judgement of the PK scientist, e.g. non-plausible concentrations). All subjects within the PK analysis set will be included in the PK data analysis. PK samples from subjects treated with MJJ821 will be measured and PK samples from placebo treated subjects will not be measured.

[REDACTED]

[REDACTED]

[REDACTED]

[REDACTED]

[REDACTED]

[REDACTED]

[REDACTED]

[illegible]

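### Protocol 9.1.1 stops PK sampling for Core Period discontinuers without a visible exception for an infusion already given, so someone stopped on Day 1 loses the 24 h sample and a shortened AUClast enters the summary by default

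*Protocol*

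**What the plan says.** Protocol 9.1.1 sets the follow-up after treatment is stopped: "Participants who discontinue study treatment during the Core Period should return at every scheduled visit" until the end of the six-week Core Period. Planned assessments are kept, with listed exceptions, among them "no PK sampling collection, and all assessments that are repeated several times in one day should be done only once". Redacted text follows directly. The sentence on the retreatment phase is separate ("Participants who discontinue study retreatment during the Extension Period should return for the End of Relapse visit") and carries no PK exception.

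The same section lists reasons for stopping that can arise soon after an infusion starts. One is "Severe hypersensitivity reaction such as anaphylaxis". Others follow the words "Study treatment should also be discontinued for any one of the following treatment-emergent events" and include limits for QTcF, heart rate, QRS, arrhythmia, heart block and post-dose blood pressure. Shortening one infusion is a different matter: "Discontinuation of study treatment may or may not include study drug infusion interruption".

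On PK, Protocol 8.5.3 states: "Following first infusion, AUClast, Cmax, Tmax, and if feasible T1/2 will be determined from the plasma concentration-time data". Later infusions yield only Cmax and Tmax. Protocol Table 12-2 ends AUClast at the last measurable concentration. Protocol 8.5.3 also asks for PK samples in all patients, to protect the blind.

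SAP 2.1.3 admits anyone with one evaluable concentration to the PK set and adds: "All subjects within the PK analysis set will be included in the PK data analysis". SAP 2.7 uses every concentration with a recorded elapsed time for parameter estimation. It sets no minimum profile length.

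**The concern.** The exception suits later visits at which no infusion is given. Its wording also reaches the Day 2 visit of someone taken off treatment on Day 1, whose 24 h sample belongs to an infusion already received. Protocol 8.5.3 pulls the other way, and sites have no rule for choosing between the two.

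AUClast after the first infusion is a named secondary endpoint, and PK is one input to dose selection at the interim analysis (Protocol 4.4 and 12.7, SAP 2.11). A profile that ends at 4 h is not comparable with one that ends at 24 h, and averaging them pulls the arm summary down. The loss is also selective. It falls on participants stopped early, including those with acute reactions, for whom late exposure is informative. Protocol 6.2.1 allows CYP2D6 inhibitors although simulated AUC rises up to 2-fold with strong ones.

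**Working it through.** The plan states no figure to reproduce. The check has two parts: what the rules do together, and how large the effect would be.

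**Path through the documents**

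1. Table 8-1 lists Day 2 (24 h) as a scheduled Core visit, so the 9.1.1 exception reaches it.
2. The Core PK row of Table 8-1 is not legible. A 24 h Core sample is inferred from SAP Table 2-11 (nominal times predose, 20 min, 40 min, 4 h and 24 h) and from AUC0-24h in Protocol 8.5.3 and Table 12-2.
3. Only a permanent stop after the first infusion and before the Day 2 draw affects AUClast. A stop at Day 15 or Day 29 cannot, because AUC is not derived for those infusions.
4. Protocol 3.2 requires at least 24 h in hospital after the Day 1 infusion, so the draw is normally feasible.
5. AUClast then ends at the last measurable sample, at the latest 4 h, and SAP 2.1.3 and 2.7 keep it.

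**Size**

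Inputs from the documents: 40-minute infusion (Protocol 6.7.2); sampling times above; linear trapezoidal rule (Protocol 8.5.3); 30 participants per arm (Protocol 12.8.1), hence 60 when the two regimens of 0.048 or 0.16 mg/kg are combined, as SAP 2.7 also does.

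Assumptions: one compartment; half-life 2 to 12 h; the 24 h value is measurable; the affected participant would otherwise have the arm's average AUC.

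With T = 2/3 h, k = ln 2 / half-life, and concentration in units of dose/volume:

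- during infusion: C(t) = (1 − e^(−kt)) / (kT)
- afterwards: C(t) = C(T) × e^(−k(t−T))
- each trapezoid: (t2 − t1) × (C1 + C2) / 2

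Example, half-life 6 h (k = 0.1155). The concentrations at 0, 20 min, 40 min, 4 h and 24 h are 0, 0.4905, 0.9625, 0.6549 and 0.0650.

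- 0 to 20 min: 0.082
- 20 to 40 min: 0.242
- 40 min to 4 h: 2.696
- 4 to 24 h: 20 × (0.6549 + 0.0650) / 2 = 7.198
- AUC to 4 h = 3.019; AUC to 24 h = 10.218; ratio r = 0.296

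One such participant among n lowers the arithmetic mean by (1 − r)/n. Here that is 0.704/30 = 2.3%, or 0.704/60 = 1.2%.

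| Half-life (h) | r | Fall, 1 of 30 | Fall, 1 of 60 |
|---|---|---|---|
| 2 | 0.446 | 1.8% | 0.9% |
| 4 | 0.337 | 2.2% | 1.1% |
| 6 | 0.296 | 2.3% | 1.2% |
| 8 | 0.269 | 2.4% | 1.2% |
| 12 | 0.237 | 2.5% | 1.3% |

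These ratios use the plan's linear rule on a sparse grid, which overstates the 4 to 24 h area. With exact integrals r is 0.719 at 2 h and 0.256 at 12 h, so at short half-lives much of the gap comes from the method. At 2 h the 24 h level is only 0.0003 of Cmax. If it falls below the 0.1 ng/mL quantification limit, AUClast ends earlier anyway and the missing draw changes nothing.

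**The case against.** The strongest reply is that the exception was never meant for the first day. It describes what happens when discontinuers return to scheduled visits, and a Day 1 participant is still in hospital. The same clause reduces assessments repeated within a day to one. Applied to the hours after a Day 1 reaction, that would conflict with the 4-hour observation in Protocol 3.2 and the 15-minute oximetry in Protocol 8.4.2. This stands for same-day samples. A reader might infer that all sampling stops at the decision and that profiles end at 40 minutes, but the documents do not support that. It does not settle the 24 h draw, because Day 2 is itself a scheduled visit.

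A reader might also infer that the rule covers everyone who stops treatment. It covers Core discontinuers; the retreatment sentence has no PK exception, and an interrupted infusion is not in itself discontinuation. Nor is exposure lost altogether, since samples taken before the decision remain.

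The redaction after the quoted words could hide a qualification, so only the absence of a visible exception can be stated.

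Last, there are partial safeguards. Protocol 8.5.3 derives parameters if the data permit, the PK scientist may exclude concentrations, and the AUC for dose proportionality is chosen for comparability across cohorts (Protocol 12.5.3). These help only in part. SAP 2.7 attaches its data condition to secondary parameters, not to AUClast. The example given for exclusion is implausible concentrations, which those in a shortened profile need not be. The comparability rule does not govern the AUClast summary.

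**Conclusion.** The point holds as a narrow, cheaply repaired flaw. As written, 9.1.1 removes the 24 h PK sample from a participant permanently stopped between the first infusion and the Day 2 visit, and the SAP by default summarises the resulting short AUClast with the full ones. Under the assumed half-life of 2 to 12 h, that AUClast is about 24% to 45% of the 0-24 h value. The arm mean falls by about 2% to 2.5% per case in 30, or about 1% per case in 60.

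The number of cases is not given and is probably small. A reader might infer that the dose decision would be distorted. Nothing in the documents shows that: the decision rests on MCP-Mod, sustained efficacy, safety and PK together, and shifts of this size are modest. The main loss is late exposure data in people who reacted acutely, which cannot be recovered afterwards. The conclusion depends on the inferred 24 h Core draw, a measurable 24 h value, and the redacted text containing no exception.

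**What to change.** In Protocol 9.1.1, limit the PK exception to infusions that are not given. State that the remaining scheduled PK samples for an infusion already started, including the 24 h sample after the first infusion, are still collected where feasible and consented. This also removes the tension with Protocol 8.5.3.

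In SAP 2.7, state that when the scheduled last sample was not taken, AUClast is listed but left out of the summary statistics, or is summarised separately.

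The cost is one sentence in each document, one extra blood draw in a few participants who are normally still in hospital, and slightly fewer AUClast values in the summary.
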